As physical exercise can increase multifidus muscle performance and it has beneficial impact in MS, we propose a pilot study to evaluate the feasibility of a home-exercise program for the diagnosis and treatment of low back pain in MS patients focused on the multifidus muscle. If shown to be feasible, this novel tool can be taught in person or in online appointments, adding to the care of MS patients.

Specific Aims

We propose a pilot study to evaluate the feasibility of a home-exercise program for the treatment of low back pain in MS patients that are not pregnant or do not have a prior diagnosis of lumbar radiculopathy or fibromyalgia. This novel tool would target the multifidus muscle and could be taught in person or in online appointments.

Aims/Objectives

- Primary aim: study the feasibility of a home-exercise program in patients with MS younger than 50 years old with expanded disability status scale (EDSS) between 1.5 to 5.5.⁸ Feasibility will be evaluated by the percentage of patients that finish the study as also by the compliance measured in hours with the home-exercise program.
- Secondary aim: qualify the multifidus dysfunction in patients with MS through evaluation of the cross-section area of the multifidus muscle measured by ultrasound at the beginning and end of the study, and by physical exam maneuvers (multifidus lift and prone instability tests).

Title: Pilot Project for Multifidus Muscle Evaluation in Patients with Multiple Sclerosis and Back Pain
PI: [name] [name]
Institution: University of Arkansas for Medical Sciences

- Exploratory aim: Evaluate the relation between compliance with the home-exercise program and the change in the cross-section area of the multifidus muscle and the change in pain score using PROMIS scale.⁹

Study Design and Procedures

This is a prospective pilot project to evaluate the feasibility of a home-exercise program to improve the function of the multifidus muscle with the intention to decrease back pain in patients with Multiple Sclerosis. Figure 1 summarizes the study design and procedures.

[figure not shown]

Figure 1

PROMIS: Patient-Reported Outcomes Measurement Information System, US : ultrasound, PE: Physical exam, PT: physical Therapy.

Adult patients with MS and back pain, further described in the study population section, will be asked to participate in this study during an appointment with their neuro-immunologist. It is standard of care to refer patients with back pain to the pain clinic.

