After patient consent at the neuro-immunology appointment, the study participant will be contacted by UAMS Pain clinic staff for an appointment. In that appointment, the participant will fill PROMIS scale that evaluates patient's quality of life, depression symptoms and pain levels. It is standard of care to ask patients regarding pain and how pain affects their mood and their daily life. In this study, we are standardizing those questions with PROMIS scale.

Next, the participant will undergo a physical exam that will include standard of care physical exam plus physical maneuvers that evaluate multifidus muscle performance. After that, a physical therapist, who is a pain clinic staff, will teach a series of exercises focused at this muscle. This is not standard of care, and it is specific for the patients that are enrolled in this study.

Title: Pilot Project for Multifidus Muscle Evaluation in Patients with Multiple Sclerosis and Back Pain
PI: [name] [name]
Institution: University of Arkansas for Medical Sciences

On the same day, an ultrasound will measure the cross-section of the multifidus muscle. It is standard of care for patients in the pain clinic undergo ultrasound, for the participants in this clinical trial, we will include the multifidus muscle measurements.

After 3 months of home exercise, but not more than 4 months from the consent, the patient will return to repeat the same evaluations, with the same staff.

Office visits (including physical exam, ultrasound and the PROMIS scale) and physical therapy services are considered routine care for this patient population. Data will be collected from patient medical record for research.

The study will be closed for recruitment after ten patients complete the final assessment. Data analysis will then start. Medical charts will be reviewed in all patients that gave consent. The review of the medical charts will finish after one year of study enrollment. Therefore, patient participation will be less than 2 years.

Study Population

Patients following in the two neuro-immunology clinics at UAMS will be recruited to this study. It is protocol in the neuro-immunology clinic to ask patients with MS about pain. An email to other UAMS neurologists as also neurologists that are outside of UAMS will be sent to advertise that UAMS will be providing this pilot project. If their patients want to participate to this program, a referral will be needed for those patients to be seen in the neuro-immunology clinic.

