
The study population will comprise of adult patients with MS who have back pain and that are following at the neuro-immunology clinic at University of Arkansas for Medical Sciences (UAMS). We anticipate including up to 10 participants in this pilot study.

Inclusion criteria:

- confirmed diagnosis by an UAMS neuro-immunologist of relapsing-remitting MS or primary progressive MS or secondary progressive MS
- Age between 18 years old and 50 years old on consent
- Complain of low back pain or severe axial back pain
- English-speaking

Exclusion Criteria:

- Patients that also have the diagnosis of thoracic or lumbar radiculopathy or history of prior thoracic or lumbar spinal surgery.
- Patients that are currently pregnant.

Title: Pilot Project for Multifidus Muscle Evaluation in Patients with Multiple Sclerosis and Back

Pain

PI: [name] [name]

Institution: University of Arkansas for Medical Sciences

- EDSS over 5.5 or less than 1.0
- Patient younger than 18 years old or older than 50 years old
- Knee total extension of less than 100 degrees

Risks and Benefits

A risk to study participants is the potential for loss of confidentiality of study data.

Measures to protect the confidentiality of study data will be implemented as described in the Data Handling and Recordkeeping section below.

Another potential risk is discomfort during the home-exercises. This will be low-risk. All exercises are low impact, and they will be taught by a physical therapist and can be reviewed and any moment through an app that patient will download.

Potential benefits include decrease in low back pain and improve in stabilization of the spine and in balance, as gait.

Data Handling and Recordkeeping

The Principal Investigator will carefully monitor study procedures to protect the safety of research subjects, the quality of the data and the integrity of the study.

When a participant enrolls in the study, a registration form will be completed by the physical therapist in their appointment. A study file containing the subject's name, medical record number, date of birth, sex, phone number, and address will be created. All study participant materials will kept at the Stephen's Spine Center. All questionnaires answered will be scanned into the participants' study files and electronic medical chart. Data will be collected from the patient's medical record.

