A password-protected electronic file in a safe digital UAMS-maintained server will be used to store and manage data that include demographics, relevant personal information, diagnosis, current and prior treatments, and questionnaire results. The Principal Investigator, [name], will carefully monitor study procedures to protect the safety of research subjects, the quality of the data, and the integrity of the study. Six months after the study has been completed, information will be de-identified and stored in a safe digital UMAS-maintained server.

Data Analysis

Since this is a feasibility study, power analysis was not conducted.

Specific Aim 1: Primary aim: study the feasibility of a home-exercise program in patients with MS younger then 50 years old with expanded disability status scale between 1.5 to 5.5.

Title: Pilot Project for Multifidus Muscle Evaluation in Patients with Multiple Sclerosis and Back Pain
PI: [name] [name]
Institution: University of Arkansas for Medical Sciences

Data Analysis Strategy: Analysis will be descriptive. Feasibility will be evaluated by the percentage of patients that finish the study as also by the compliance in logged hours of exercise.

Specific Aim 2: qualify the multifidus dysfunction in patients with MS through evaluation of the cross-section area of the multifidus muscle measured by ultrasound at the beginning and end of the study, and by multifidus lift test and prone instability)

Data Analysis Strategy: As there is no literature in the evaluation of multifidus muscle in patients with MS, this will be a qualitative description of cross-section area and muscle performance on physical exam.

Specific Aim 3: Evaluate the relation between compliance with the home-exercise program and the change in the cross-section area of the multifidus muscle and the change in pain score using PROMIS Scale. Variables to also be considered will be EDSS of the patient.

Data Analysis Strategy: multiple linear regression will be used to evaluate if there is an association between the change in the multifidus cross-section area with compliance with home-exercise program, EDSS and pain level. ROC curve analysis will be done evaluating average hours of exercise per week and change in the cross-section area of a muscle.

This pilot project will end after 10 patients finish the home-exercise program of after one year.

Ethical Considerations

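### Exploratory Aim 3 fits three predictors to about 10 patients without guarding against over-reading the fit, and it uses pain level as a predictor although change in pain is one of the aim's outcomes

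*Combined protocol and SAP*

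**What the plan says.** Under Aims/Objectives the aim is labelled exploratory: "Exploratory aim: Evaluate the relation between compliance with the home-exercise program and the change in the cross-section area", together with the change in PROMIS pain score. The strategy under Data Analysis, Specific Aim 3, is that "multiple linear regression will be used to evaluate if there is an association between the change in the multifidus cross-section area". Three predictors are listed: exercise compliance, the EDSS score and the level of pain. The same section names EDSS as a further variable to consider.

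Three statements bear on the number of patients:
- Study Population: "We anticipate including up to 10 participants in this pilot study".
- Study Design and Procedures: "The study will be closed for recruitment after ten patients complete the final assessment".
- End of Data Analysis: "This pilot project will end after 10 patients finish the home-exercise program of after one year".

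Data Analysis also states: "Since this is a feasibility study, power analysis was not conducted". The plan does not mention confidence intervals, R-squared of either kind, a limit on the number of predictors, or a simpler lead model. It does not say whether pain level is the baseline score, the final score or the change.

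**The concern.** Three predictors and an intercept use four parameters on about ten records. A model of that size fits noise well, and the usual summary of fit, unadjusted R-squared, does not show it. A reader planning the next study could take a chance fit as evidence that exercise, disability and pain account for much of the muscle change. The relation that the aim states is between compliance and change, and each added term takes one of few degrees of freedom from that estimate.

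The role of pain is a separate difficulty. The aim asks how compliance relates to change in area and to change in pain. The strategy instead puts pain on the predictor side of the area model and gives no analysis with pain change as the outcome. If the pain term is a final or change score, exercise may have affected it, and holding it fixed could remove part of the effect being sought.

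**Working it through.** The plan states no power, effect size or expected fit, so there is no figure of its own to reproduce.

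**Inputs.** Predictors: k = 3 (Data Analysis, Specific Aim 3), taken as one linear term each. Only patients with both ultrasounds have a change value. The size statements give about n = 10 at most. Dropout among up to 10 included, or the one-year stop, would give fewer. Assumed, not in the documents: n = 7 as a low case, two-sided 5% level, normal errors and predictors.

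**Residual degrees of freedom**, n − k − 1:
- n = 10: 10 − 4 = 6 with three predictors; 10 − 2 = 8 with one.
- n = 7: 7 − 4 = 3 with three; 7 − 2 = 5 with one.

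**Chance fit.** With no association, R-squared follows Beta(k/2, (n − k − 1)/2), with mean k/(n − 1).

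| n | predictors | mean R-squared | P(R-squared > 0.5) |
|---|---|---|---|
| 10 | 3 | 3/9 = 0.33 | 22% |
| 10 | 1 | 1/9 = 0.11 | 2% |
| 7 (assumed) | 3 | 3/6 = 0.50 | 50% |
| 7 (assumed) | 1 | 1/6 = 0.17 | 8% |

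At n = 10 the three-predictor R-squared must exceed 0.70 before the overall F test reaches p < 0.05. A value of 0.5 can therefore look substantial and be quite compatible with no association.

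**What is not distorted.** In simulation under no association (40,000 data sets per setting), adjusted R-squared averaged about 0. The compliance slope test rejected in 5% of data sets with either one or three predictors.

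**Precision of the compliance slope.** The 95% half-width is t(0.975, df) × s / √[SSx(1 − R²x)]. Here s is the residual SD, SSx is the sum of squares of compliance about its mean, and R²x is the R-squared of compliance on the other predictors. At n = 10:
- The t multiplier rises from 2.306 to 2.447, a ratio of 1.06.
- Two unrelated covariates inflate the slope variance on average by (n − 3)/(n − 5) = 7/5 = 1.4, because they correlate with compliance by chance.
- As a rough guide, 1.06 × √1.4 = 1.25. Simulation gives somewhat less: a median width ratio of 1.21 and a ratio of mean widths of 1.22.

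The ratio depends on how much of the area change EDSS and pain explain. With covariates independent of compliance, the ratio of mean CI widths, three predictors to one, is:

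| Variance explained by EDSS and pain | n = 10 | n = 7 |
|---|---|---|
| 0% | 1.22 | 1.60 |
| 20% | 1.09 | 1.43 |
| 30% | 1.02 | 1.34 |
| 40% | 0.95 | 1.24 |
| 50% | 0.86 | 1.13 |
| 60% | 0.78 | 1.01 |

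The break-even point is about 30-35% at n = 10 and about 60% at n = 7.

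**Absolute precision.** At n = 10 with no covariate effect, the median half-width is 0.76 outcome SD per predictor SD with compliance alone and 0.91 with three predictors. Both are wide.

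**Cost of not adjusting.** With all predictors correlated at 0.3, EDSS and pain explaining 30% of the outcome and no true compliance effect, the one-predictor slope test rejects in 8.4% of data sets at n = 10. The three-predictor test rejects in 5.0%.

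**The case against.** The strongest reply is that the aim is exploratory, no power is claimed, no decision depends on this model, and the descriptive feasibility result is untouched. All of that stands, and it limits the point to interpretation of a secondary table.

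Four stronger readings are tempting, and the documents do not support them:
- **The report will show a misleading R-squared.** The plan never mentions R-squared. The supported statement is that nothing in the plan guards against over-reading it if it is reported.
- **Small n inflates false positives.** It does not: the slope test keeps its 5% level.
- **Half the variance will appear explained by chance.** That needs an assumed 7 records. With ten completers the average is one third.
- **The extra terms waste precision.** This holds only if they explain little of the area change. The documents give no such share, and above roughly a third at n = 10 adjustment helps.

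It is also fair to say that EDSS is named deliberately. If it relates to both compliance and area change, the unadjusted slope is confounded, and a narrower interval around it is no gain. Sample size, more than model size, is the main limit. These arguments justify keeping an EDSS-adjusted slope in view. They do not justify an undefined pain term in the area model.

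**Conclusion.** The point holds as a cheap improvement to an exploratory analysis and does not amount to a design flaw. At n = 10, chance alone gives the planned model an average unadjusted R-squared of 0.33 and a 22% probability of exceeding 0.5; compliance alone gives 0.11 and 2%. The chance-fit figures rest on normal errors, linear terms and no true association.

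The precision cost, about 21% in CI width at n = 10, further assumes that EDSS and pain explain little of the outcome and are unrelated to compliance. It should be quoted only with that condition. Neither model will give a precise compliance slope. The objection to pain level needs no arithmetic: it follows from the aim listing pain change as an outcome and from the plan leaving the predictor undefined.

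**What to change.** In the Data Analysis Strategy for Specific Aim 3:

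1. Make the lead result the slope of area change on compliance, with a 95% CI and a scatter plot on which each patient's EDSS is marked.
2. Report the EDSS-adjusted slope with its 95% CI beside it. At n = 10 this leaves 10 − 3 = 7 residual degrees of freedom.
3. Remove pain level from the area model. Analyse change in PROMIS pain on compliance as its own outcome, in the same way. This answers the part of the aim that the current strategy leaves without a model.
4. If any multi-predictor fit is shown, give adjusted rather than raw R-squared and label it exploratory.

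The change is a short rewrite of analysis text and needs no new data or patients. Its downside is that the lead slope is open to confounding by EDSS, which is why the adjusted slope belongs next to it.

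### The ROC analysis in exploratory Aim 3 relates two continuous variables with no binary state, cut-off or classifier defined; a plot, Spearman's correlation and a slope should replace it

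*Combined protocol and SAP*

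**What the plan says.** The Aims/Objectives section words the aim as one of association: "Exploratory aim: Evaluate the relation between compliance with the home-exercise program and the change in the cross-section area of the multifidus muscle". PROMIS pain is named there as a second outcome. Under Data Analysis, Specific Aim 3, two methods follow. The first treats area change as a continuous outcome: "multiple linear regression will be used to evaluate if there is an association between the change in the multifidus cross-section area with compliance", with EDSS and pain level as further predictors. The second is the ROC: "ROC curve analysis will be done evaluating average hours of exercise per week and change in the cross-section area of a muscle".

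Both ROC variables are continuous. Exercise enters Aim 1 as "compliance in logged hours of exercise", and Aim 2 uses the "cross-section area of the multifidus muscle measured by ultrasound at the beginning and end of the study". Nowhere does the document define a responder, a minimum change in area or a threshold for adequate exercise, or say which variable is the classifier. Under Aim 2 it offers no outside basis for a cut either: "As there is no literature in the evaluation of multifidus muscle in patients with MS".

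On size, the Study Population section says "We anticipate including up to 10 participants in this pilot study", and the Data Analysis section closes with "This pilot project will end after 10 patients finish the home-exercise program of after one year". The ROC would therefore have about 10 patients, or fewer if the time limit comes first.

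**The concern.** A ROC curve plots sensitivity against one minus specificity, and neither exists until patients are sorted into two classes. The sentence names two measurements and no classes. The order of the words suggests hours as the score and area change as the outcome, but the plan does not say so.

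Two things are at stake. The missing cut could be chosen once the results are known, and the AUC would then depend on that choice. Even with a cut fixed beforehand, dichotomising discards information in a very small sample, although the aim asks about a relation and the adjacent regression already keeps area change continuous. The Dissemination of Data section foresees publications, so such an AUC could be reported.

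**Working it through.** The plan gives no AUC, cut-off, effect size or power figure, so there is nothing of its own to reproduce. The inputs are n = 10 (from the sections above; all 10 assumed to have both scans) and the assumed splits, AUCs and correlations stated below.

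**1. Precision with a cut fixed in advance.** The Hanley-McNeil variance with m positives and k negatives is

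SE² = [A(1−A) + (m−1)(Q₁−A²) + (k−1)(Q₂−A²)] / (mk), where Q₁ = A/(2−A) and Q₂ = 2A²/(1+A).

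For A = 0.70: A(1−A) = 0.21, Q₁−A² = 0.5385−0.49 = 0.0485, and Q₂−A² = 0.5765−0.49 = 0.0865. At 5/5, SE² = (0.21 + 4×0.0485 + 4×0.0865)/25 = 0.0300, so SE = 0.173.
- Wald 95% CI: 0.70 ± 1.96×0.173 = 0.36 to 1.04, truncated at 1.00.
- Logit-scale 95% CI: ln(0.7/0.3) = 0.847 and SE = 0.173/0.21 = 0.825, giving 0.32 to 0.92.
- For unequal splits the SE depends on which group is positive: 0.179 (7 positive, 3 negative) or 0.198 (reversed); 0.199 (8 and 2) or 0.232 (reversed).

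**2. No true relation, split fixed in advance.** All orderings of the labels are equally likely. At 5/5, AUC ≥ 0.70 occurs in 39 of 252 (15.5%) and AUC ≥ 0.80 in 19 of 252 (7.5%). For AUC ≥ 0.70, the 6/4, 7/3 and 8/2 splits give 37/210 (17.6%), 23/120 (19.2%) and 9/45 (20.0%).

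**3. No true relation, cut on area change picked to give the largest AUC.** Counted over all 10! = 3,628,800 orderings:

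| Minimum per group | Cuts available | AUC ≥ 0.70 | AUC ≥ 0.80 |
|---|---|---|---|
| 4 | 3 | 28.8% | 12.3% |
| 3 | 5 | 39.3% | 20.5% |
| 2 | 7 | 48.8% | 31.7% |

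**4. Dependence on the cut when a relation exists.** In 5,000 simulated data sets with an assumed correlation of 0.5 and at least 2 patients per group, the lowest AUC within a data set had median 0.56 and the highest 0.94. The median range was 0.32.

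**5. A natural pre-set cut can fail.** Take increase versus no increase. The chance that the smaller group holds 0 or 1 patient is P(X ≤ 1) + P(X ≥ 9), with X binomial (10, p). It is 2% for p = 0.5, 15% for p = 0.7 and 38% for p = 0.8 (p assumed).

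**6. If an hours threshold were read off the curve** (the plan does not propose this), the best Youden index at a fixed 5/5 split would average 0.31 with no relation at all.

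**7. Cost of dichotomising.** At nearly equal exact test size, the 5/5 Wilcoxon/AUC test (0.032) and Spearman with |r| ≥ 0.697 (0.031) were compared in 200,000 bivariate normal samples. Power is 14% against 20% at a true correlation of 0.5, and 30% against 47% at 0.7.

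**8. The alternative at n = 10.** For an observed Spearman correlation of 0.5, the Fisher z interval is tanh(0.549 ± 1.96/√7) = −0.19 to 0.86. With the Bonett-Wright SE, √((1+r²/2)/(n−3)), it is −0.23 to 0.87. The standardised slope at 0.5, with t on 8 degrees of freedom, has a CI of −0.21 to 1.21.

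**The case against.** The best reply is that this is the second analysis of an exploratory aim in a feasibility pilot with no power calculation, that the primary aim is purely descriptive, and that nothing done to a patient depends on it. That is true, and it limits the weight of the point.

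The defect could also be cured by specifying the ROC instead of replacing it, or by deleting the sentence, since the regression already addresses hours and area change. Both are legitimate. Specification, however, needs a justified cut that the document has no source for, and step 5 shows that even the obvious one may leave nothing to analyse. Deletion leaves only the regression, whose three predictors leave 10 − 4 = 6 residual degrees of freedom, and no simple picture of the relation.

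The larger error rates in step 3 assume conduct the plan does not describe: a search over all cuts with the best one reported. They show what the wording leaves open, not what the sponsor intends. With a cut fixed in advance, 15.5% is ordinary small-sample noise.

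Finally, the alternative is noisy too. With no relation and n = 10, a Spearman correlation of at least 0.35 occurs in about 16% of studies. The gain in power is small at a correlation of 0.5, and the larger gain rests on an assumed 0.7. The case for replacement is therefore that the method is computable, needs no arbitrary choice and fits the aim. It would not make the result precise.

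**Conclusion.** The concern holds. The ROC analysis cannot be carried out as written, because no binary state, cut-off or classifier is defined for the two continuous variables, and it does not match an aim about a relation. Under the assumption of 10 patients with both scans, a pre-set 5/5 split gives an AUC so imprecise (0.36 to 1.00 around 0.70) that it is close to uninformative. An open choice of cut can raise the chance of an AUC of at least 0.70 under no relation from 15.5% to between 29% and 49%. The splits, correlations, shares increasing and 95% level are assumptions, since the document gives none. The consequence is confined to the exploratory aim; the feasibility conclusion stands either way. It should be corrected, but it is no obstacle to the study.

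**What to change.** Replace the ROC sentence with:

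> Individual change in cross-section area will be plotted against average weekly hours of exercise, with Spearman's correlation and the unadjusted slope (area change per hour per week), each with a 95% CI. This is descriptive and complements the regression; no hours threshold will be derived.

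Second best, if the sponsor has a reason to keep the ROC: before any follow-up scan is read, name the classifier and the binary state with a rationale, set a minimum group size below which no AUC is reported, give the AUC with its CI as description only, and derive no threshold. Deleting the sentence is the minimum cure.

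The cost is one sentence, with an IRB amendment if required, and no new data. No AUC would be reported, and the unadjusted slope partly overlaps the compliance coefficient of the planned regression, so the report should state how the two differ (unadjusted against adjusted for EDSS and pain level).
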